4.1.4. Study Participants

4.1.4.1. Disposition of Participants

A clear accounting of the disposition of all participants who enter the study will be provided, from the time of informed consent to study completion. Only the pooled numbers will be provided for screened, screen failures, and reasons for screen failures.

The number and percentage of the participants in the following categories will be summarized separately by study part (interventional and non-interventional [observational]) for all participants signed the ICF:

- Participants signed ICF.
- Participants screened for Screening part 1.
- Participants screened for Screening part 2.
- Participants with screen failure and reasons for screen failures in each screening part.
- Did not receive treatment with reasons for not receiving the treatment (only for interventional part).
- Completed study treatment (only for interventional part).

- Did not complete study treatment with reasons for premature discontinuation of study drug (only for interventional part).
- Completed study.
- Did not complete the study with reasons for premature discontinuation of study.

The denominator for the percentage calculation will be the total number of participants in the Full Analysis Set.

A by-participant listing of all screen failures and study eligibility details will be presented for the screened population. The reasons for premature study discontinuation will be listed by PID. The reasons for screen failure will also be provided by study part, by PID number in ascending order.

4.1.4.2. Protocol Deviations

A protocol deviation is any noncompliance with the clinical trial protocol, ICH GCP, or SOP requirements. The noncompliance may be either on the part of the participant, on the Investigator, or on the study site staff. Protocol deviations occurring after participants entered the study are documented during the routine monitoring. These protocol deviations will be classified as “major” or “minor” on a case-by-case basis by the clinical study team and sponsor.

Major protocol deviations are defined as those deviations from the protocol likely to have an impact on the participant’s right, safety, well-being, and/or validity of the data for analysis. Minor protocol deviations included all deviations from the protocol excluding the major protocol deviations. Major protocol deviations and any action to be taken regarding the exclusion of participants or affected data from specific analysis are defined in the Protocol Deviation Assessment Plan (PDAP).

Deviations considered to be major will be listed. All decisions on importance will be made ahead of database lock for the primary analysis and will be documented prior to the primary analysis being conducted.

A summary of major protocol deviations for FAS, by deviation category will be provided.

4.1.4.3. Analysis Sets

The number and percentage of participants in each analysis set and reasons for exclusions from each analysis set will be summarized for FAS. The participants included and excluded in each analysis set will be listed for FAS.

4.1.4.4. Demographics and Baseline Characteristics

The maternal demographic and baseline data will be collected at the screening visits.

The demographic characteristics (e.g., age, race, ethnicity, sex, height, body weight, body mass index [BMI]) and baseline viral serology (Hepatitis B virus surface [negative/positive], Hepatitis C virus antibody [negative/positive], Human Immunodeficiency Virus antibody [negative/positive]), FNAIT status (maternal HPA-1 genotype [HPA-1b/b, HPA-1a/a, HPA-1a/b], maternal HLA-DRB3*01:01 genotype [positive, negative], maternal anti-HPA-1a antibody [positive, negative], fetal HPA-1 genotype [HPA-1a/b, HPA-1b/b])) results will be summarized and listed for FAS.

4.1.4.5. Medical History

Medical history collected at screening will be coded using MedDRA version 27.0 or later.

Medical history will be summarized by SOC and by preferred term for FAS. Participants who report two or more medical history items that are coded to the same SOC and preferred term will be counted only once by the unique coded term in the summary.

A listing of medical history will be provided for FAS.

4.1.4.6. Obstetrics History

The obstetrics history (participants with previous pregnancies [Yes, No], and for each prior pregnancy - mode of delivery [vaginal, cesarean section], gestational age of delivery, outcome of delivery [premature birth, live birth, still birth, spontaneous abortion, elective abortion]) collected at screening will be summarized and listed for FAS.

4.1.4.7. Prior and Concomitant therapy

Standard treatments given during obstetric care are allowed during the study. Any medication (including over-the-counter or prescription medicines, recreational drugs, vitamins, and/or herbal

supplements) or other specific categories of interest that the participant is receiving at the time of enrollment or receives during the study will be recorded along with:

- Reason for use
- Dates of administration including start and end dates
- Dosage information including dose and frequency

Concomitant medications will be considered on a case-by-case basis by the investigator in consultation with the medical monitor.

For the purpose of inclusion in prior and/or concomitant medication summaries, incomplete medication start and stop dates will be imputed as detailed in [section 4.1.3.4.](#)

- Prior medications: Medications taken prior to study treatment with a stop date prior to first dose of study treatment.
- Concomitant medications: Medications with a stop date on or after the first dose date of study treatment (and could have started prior to or during treatment).

Prior and concomitant therapies will be summarized and listed separately for FAS. Both prior and concomitant therapy will be summarized by ATC drug class level 4 and by ATC drug class level 1 for preferred name using the number and percentage of participants. A participant reporting the same medication more than once will be counted once within each preferred name. The summary will be ordered alphabetically by ATC 4 drug class, and by preferred drug name in order of descending frequency within each ATC 1 drug class. For drugs with the same frequency, sorting will be done alphabetically.

4.2. Primary Endpoint Analysis

4.2.1. PK Profile of RLYB212 During Pregnancy Following Repeat SC Administration

4.2.1.1. Maternal RLYB212 Concentrations

Serum samples will be collected from participants for measurement of concentrations of RLYB212 at regular intervals as specified in [Table 3.](#)

The RLYB212 concentration data will be reviewed combined with dosing, concomitant medication and AE data on a case-by-case basis to determine whether any exclusion from the PK analysis set is deemed necessary.

Serum concentration-time data will be summarized for RLYB212 PK analysis set for interventional participants, by analysis visit, by means of descriptive statistics as follows:

- Geometric mean (gmean, calculated as $\exp[\mu]$, where μ is the mean of the data on a logarithmic scale).
- Coefficient of variation (gCV%, calculated as $100 (\sqrt{\exp^2} - 1)$ where s is the standard deviation of the data on a log scale).
- Gmean \pm geometric standard deviation (gmean+gSD and gmean-gSD), calculated as $\exp[\mu \pm s]$).
- Arithmetic Mean.
- SD.
- Median.
- Minimum (min).
- Maximum (max).
- Number of observations (n).
- $n > \text{LLOQ}$.

Individual serum concentration versus actual elapsed times will be presented by scatter plot on both the linear and semilogarithmic scale for RLYB212 PK analysis set.

Individual concentrations below the LLOQ of the bioanalytical assay will be reported as NQ (Not Quantifiable) in the listings with the LLOQ defined in the footnotes of the relevant TFLs.

Individual serum concentrations that are 'Not Reportable' will be reported as NR and those that are missing will be reported as NS (No Sample) in the listings. Serum concentrations that are NQ, NR, or NS will be handled as follows for the provision of descriptive statistics:

- Missing or below LLOQ (BLQ) PK results prior to the first dose of RLYB212 will be imputed as zero for graphing and descriptive statistics of concentrations. Post-dose concentration values that are BLQ or missing values (e.g., no sample collected, or no value reported from bioanalytical assay) will be treated as missing.

- At a time point where less than or equal to 50% of the concentration values are NQ, all NQ values will be substituted with the LLOQ concentration, and all descriptive statistics will be calculated accordingly.
- At a time point where more than half (but not all) of the values are NQ, mean, gmean, gCV%, +gSD and SD will be set to NC (Not Calculated). The maximum value will be reported from the individual data and the minimum and median will be set to NQ.
- If all concentrations are NQ at a time point, the mean, gmean, min, median and max will be reported as NQ and the +gSD, gCV%, and SD will be reported as NC.
- The number of values above LLOQ ($n > LLOQ$) will be reported for each time point together with the total number of collected values.
- Three observations $> LLOQ$ will be required as a minimum for PK serum concentrations to be summarized. Two values will be presented as minimum and maximum with the other summary statistics as NC.

RLYB212 concentrations below BLQ will be reported as 0 for all descriptive statistics summaries.

PK concentration data will be listed for each participant who receives study intervention (RLYB212), together with the flag.

4.2.1.2. Maternal Pharmacokinetics Parameters

Maternal pharmacokinetics parameters are not part of the CSR and will be presented in a supplementary report.

4.2.2. Maternal and Fetal Safety of RLYB212 During Pregnancy

4.2.2.1. Type, Seriousness, and Incidence of Maternal AEs

An adverse event is any untoward medical occurrence in a clinical study participant, temporally associated with the use of study intervention, whether or not considered related to the study intervention. An AE can therefore be any unfavorable and unintended sign (including an abnormal laboratory finding), symptom, or disease (new or exacerbated) temporally associated with the use of study intervention.

Adverse Events will be collected throughout the study from the time of screening part 2 and beyond until the end of study visit (10 weeks postpartum for the maternal participant and 4-6 weeks of age for the neonate/infant). MedDRA version 27.0 or above will be used to code the

AEs. All maternal AEs will be graded according to the National Cancer Institute of Common Terminology Criteria for AEs (CTCAE version 5.0 or higher) and Maternal and Fetal Adverse Event Terminology (MFAET version 1.0 or higher).

Serious adverse events are collected from Screening part 2 of the study and onward. Serious adverse events are identified as serious via the eCRF.

- All AEs: An AE that newly occurs or worsen in severity from the time of screening part 2.
- TEAEs: An AE that newly occurs or worsen in severity on or after the first dose of the study drug.
- SAE: An AE occurring during any study phase, that fulfils one or more of the following criteria:
 - Results in death.
 - Is life-threatening.
 - Requires in-participant hospitalization or prolongation of existing hospitalization.
 - Results in persistent or significant disability or incapacity.
 - Is a congenital anomaly or birth defect.
 - Is an important medical event that may jeopardize the participant or may require medical treatment to prevent one of the outcomes listed above.

All reported AEs, SAEs will be listed along with the actual dose received at the time of onset, date of onset, date of resolution (if AE is resolved), investigator's assessment of CTCAE grade, MFAET grading, relationship to study treatment, action taken and outcome. The numbers and percentage of participants (with 95% Clopper-Pearson confidence interval) experiencing AEs/TEAEs will be summarized separately (AEs and TEAEs will be summarized separately) for the SAS, including but are not limited to:

- All AEs (*).
- All AEs related to study treatment (*).
- All AEs related to study procedure (*).
- All AEs with outcome of death.
- All AEs with outcome of death, related to study treatment.
- All AEs with outcome of death, related to study procedure.
- All AEs leading to drug interruption (*).
- All AEs leading to drug interruption, related to study treatment.

- All AEs leading to drug interruption, related to study procedure.
- All AEs leading to drug discontinuation (*).
- All AEs leading to drug discontinuation, related to study treatment.
- All AEs leading to drug discontinuation, related to study procedure.
- All AEs leading to study discontinuation (*).
- All AEs leading to study discontinuation, related to study treatment.
- All AEs leading to study discontinuation, related to study procedure.
- AEs of CTCAE grade 3 or higher (*).
- AEs of CTCAE grade 3 or higher, related to treatment.
- AEs of CTCAE grade 3 or higher, related to study procedure.
- AEs of MFAET grade 3 or higher.
- AEs of MFAET grade 3 or higher, related to treatment.
- AEs of MFAET grade 3 or higher, related to study procedure.
- All SAEs (*).
- All SAEs, related to study treatment (*).
- All SAEs, related to study procedure.
- All SAEs with outcome of death.
- All SAEs with outcome of death, related to study treatment.
- All SAEs with outcome of death, related to study procedure.
- All SAEs leading to drug interruption (*).
- All SAEs leading to drug interruption, related to study treatment.
- All SAEs leading to drug interruption, related to study procedure.
- All SAEs leading to drug discontinuation (*).
- All SAEs leading to drug discontinuation, related to treatment.
- All SAEs leading to drug discontinuation, related to study procedure.
- All SAEs leading to study discontinuation (*).
- All SAEs leading to study discontinuation, related to study treatment.
- All SAEs leading to study discontinuation, related to study procedure.

The categories marked above in * will be summarized by MedDRA System Organ Class and Preferred Term (PT). The following maternal and fetal AEs by MedDRA preferred term will be summarized separately for SAS (*Spencer R, Hecher K, Norman G, Marsal K, Deprest J, Flake A, et al.*).

Maternal AEs:

- Haemorrhage in pregnancy
- Preterm premature rupture of membranes
- Chorioamnionitis
- Anaemia of pregnancy
- Gestational hypertension
- Pre-eclampsia
- Eclampsia
- Premature labour
- Puerperal infection
- Postpartum haemorrhage (primary)
- Retained placenta or membranes
- Amniotic fluid embolism

Fetal AEs:

- Haemorrhage in pregnancy
- Preterm premature rupture of membranes
- Chorioamnionitis
- Anaemia of pregnancy
- Fetal fluid collection
- Fetal bradycardia: non-labour
- Fetal tachyarrhythmia
- Cardiac function abnormalities
- Fetal brain scan abnormal
- Fetal gastrointestinal tract imaging abnormal
- Fetal musculoskeletal imaging abnormal
- Fetal renal imaging abnormal
- Fetal movement disorders
- Fetal neoplasm
- Fetal structural abnormalities: not otherwise classified
- Abnormal fetal growth
- Fetal intraoperative injury
- Procedure haemorrhage
- Post-procedural haemorrhage

4.2.2.2. Maternal Physical Examination Findings

A complete physical examination including the following observations/measurements will be done at the time of screening part 2: height, weight, general appearance, skin, head, eyes, ears, nose, and throat, lymph nodes, heart, lungs, abdomen, extremities/joints, neurological, and mental status. Any significant abnormalities observed at screening will be recorded as medical history.

A brief physical and obstetric examination (heart, lungs, abdomen) will also be performed throughout pregnancy and the postpartum period. All physical examination findings will be summarized and listed for the SAS.

4.2.2.3. Vital Signs

Systolic and diastolic blood pressures (mmHg), heart rate (beats/minute), respiratory rate (breaths/min) and temperature (°C) will be recorded in supine position for participants from screening. Any clinically significant abnormal findings will be recorded as AEs except events identified at the Screening Part 2 visit.

Changes from baseline in vital signs to each post-baseline assessment will be calculated. Absolute values, changes from baseline and percentage change from baseline will be summarized for the SAS. Individual vital signs results will be listed for the SAS too.

4.2.2.4. Maternal Clinical Laboratory Values

Summaries for safety laboratory will be presented for the SAS, which will only include the parameters specified in [Table 5](#).

All values will be classified as low (below range), normal (within range), or high (above range) based on laboratory reference ranges. Results will be presented in PAREXEL standard units as specified in [Table 6](#) and all the clinical laboratory parameter values in collected lab units will be converted to PAREXEL standard units using the corresponding conversion factors as shown in [Table 7](#). For all continuous laboratory assessments, absolute value, will be summarized using descriptive statistics at each scheduled assessment timepoint.

If the same parameter is found as measured in serum and in plasma, then the summaries will not distinguish between them (e.g. values from plasma albumin and serum albumin will be summarized under albumin). If the same parameter is found as measured in serum and in plasma

for the same participant (which would be a rare case), then the change from baseline will only be calculated for those post-baseline values using the same source, i.e., only within plasma or serum.

For clinical chemistry, hematology and coagulation, shift tables will be presented from baseline to worst value on-treatment (defined from start of treatment to parturition) according to reference range classification (HIGH, LOW, NORMAL). A shift table from baseline to maximum value will be summarized for urine dipstick variables.

Spaghetti plots of absolute values for all hematology, coagulation and clinical chemistry parameters will also be presented.

Liver biochemistry test results over time for participants who show elevated ALT or AST ($\geq 3 \times$ ULN) and elevated bilirubin ($\geq 2 \times$ ULN) (elevated results do not need to be present at the same visit) or ALT or AST of $\geq 5 \times$ ULN, will be tabulated and plotted. Plots for both maximum post-baseline alanine transaminase (ALT) and aspartate transaminase (AST) versus the maximum post-baseline total bilirubin (expressed as multiples of their upper limit of normal [ULN] reference range) will be produced with reference lines at 3 x ULN for ALT and AST and 2 x ULN for total bilirubin (eDISH plot).

All laboratory results collected will be listed.

4.2.2.5. Maternal ECG

12-leads ECGs including heart rate, PR interval, QRS duration, QT interval, PR segment, RR interval, RR segment and QTc interval will be summarized for the SAS. In the summary table, baseline value and change from baseline at each post-baseline visit will also be provided. A listing for ECG assessment results with interpretation will be presented. The clinically significant abnormal results will be flagged in the listing.

4.2.2.6. Obstetric/Fetal Doppler Ultrasound

Obstetric and fetal doppler ultrasound monitoring will be performed as outlined in the SoA ([Table 2](#)) and at regular intervals during the study and consistent with local obstetric standard of care, to detect any evidence of placental structural abnormality, organ pathology, hemorrhage, or delayed growth in the fetus, or any doppler velocimetry effects indicative of placental insufficiency or fetal anemia.

The maternal ultrasound results (indication, fetal position, fetal anatomy with clinical significance and fetal AE, fetal cardiac activity with clinical significance and fetal AE, placenta position with clinical significance and fetal AE, placenta anatomy with clinical significance and fetal AE, amniotic fluid volume with clinical significance and fetal AE, retroplacental hemorrhage (Yes, No) with clinical significance and fetal AE, fetal growth restriction (Yes, No) with clinical significance and fetal AE, fetal macrosomia (Yes, No) with clinical significance and fetal AE and fetal doppler ultrasound findings (anatomic area, pulsatility index, resistance index, end-diastolic flow, systolic/diastolic ratio, overall impression with clinical significance, fetal AE and intervention status) will be listed only for the SAS.

4.2.3. Sensitivity Analysis

Not applicable

4.2.4. Supplementary Analyses

Not applicable

4.3. Secondary Endpoint Analysis

4.3.1. RLYB212 Exposure in the Neonate at Delivery

4.3.1.1. Concentration of RLYB212 in Cord Blood

A cord blood sample will be collected at parturition to assess neonate exposure to RLYB212. Neonate serum concentration will be listed only for all newborns for the RLYB212 PK analysis set. Serum concentrations below BLQ will be imputed as 0.

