9.4.3 Secondary Endpoints

RLYB212 exposure in the neonate will be evaluated by cord blood concentration of RLYB212, which will be a single measurement, and neonatal thrombocytopenia will likewise be evaluated by cord blood platelets.

Other aspects of safety of RLYB212 exposure in the neonate will be evaluated during the postpartum follow-up period in terms of type and seriousness and incidence of AEs, physical examination findings including APGAR scores, vital signs and cord blood levels for platelets, hematocrit, hemoglobin, reticulocytes, total bilirubin, and any additional safety testing done on the neonate on an ad hoc basis.

RLYB212 immunogenicity data and the presence of ADA, and whether there is a neutralizing response, will be determined.

Pregnancy and neonatal outcomes following antenatal RLYB212 administration will include:

- Number of spontaneous abortions, defined as non-deliberate fetal death which occurs prior to GW 19.
- Number of elective abortions, defined as deliberate termination of pregnancy at any time in gestation.
- Number of stillbirths, defined as non-deliberate fetal death anytime in gestation on or after GW 19.
- Number of premature births, defined as live birth prior to GW 37.
- Number of full term births (\geq GW 37).
- Overall health and development of infants at 4-6 weeks and 12 months of age.

- Neonatal thrombocytopenia and severe neonatal thrombocytopenia, as defined by a platelet count $< 150 \times 10^9/L$ and $< 50 \times 10^9/L$, respectively, collected as a part of the cord blood sample.

Maternal alloimmunization to HPA-1a will be determined by a measurement of maternal circulating anti-HPA antibodies at 10 weeks postpartum or 10 weeks from the date of the pregnancy-terminating event (ie, abortion [spontaneous/elective] or stillbirth).

Where possible, data will be summarized using descriptive statistics and listed.

9.4.4 *Tertiary/Exploratory Endpoints*

Not applicable.

9.4.5 *Other Safety Analyses*

All routine safety analyses will be performed on the Safety Analysis Set. Data will be presented separately for maternal participants and neonates/infants.

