4.1.3.4. Handling of Missing Data

Missing or below lower limit of quantitation (BLQ) PK results prior to the first dose of RLYB212 will be imputed as zero for graphing and descriptive statistics of concentrations. RLYB212 concentrations with missing time or date information will be considered non-evaluable, will be flagged in the data set. No formal analysis of “outliers” is planned.

No imputation of missing data will be performed except the partial date imputations specified as below:

Missing or Partial Dates

All listings will report dates as collected on the eCRF and will not include imputed dates.

Imputation Rules for Prior or Concomitant Medication Dates

Project Document Version No.:2.0; Document Effective Date: Date of last signature

TP-GDO-WW-016-09

Effective Date: 22 Dec 21

Related to: SOP-GDO-WW-019

Page 16 of 70

Missing Medication Start Date

- If the medication start date is missing, and the medication stop date is on or after the first dose of study medication, then the medication start date will be imputed as the date of the first dose of study medication.

If the medication start date is missing, and the medication stop date is not missing and before the first dose of study medication, then the medication start date will be imputed as the medication stop date.

Partial Medication Start Date

Missing Day and Month

- If the year of the incomplete start date is the same as the year of the date of the first dose of study medication, then the day and month of the date of the first dose of study medication will be assigned to the missing fields.
- If the year of the incomplete start date is before the year of the date of the first dose of study medication, then December 31 will be assigned to the missing fields.
- If the year of the incomplete start date is after the year of the date of the first dose

Missing Month Only

- The day will be treated as missing and both month and day will be replaced according to the above procedure.

Missing Day Only

- If the month and year of the incomplete start date are the same as the month and year of the date of the first dose of study medication, then the day of the first dose of study medication will be assigned to the missing day.

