4.8. Changes to Protocol-planned Analyses

Since there is a formal possibility of (all) samples reading below LLOQ, and that is important information. The description of RLYB212 PK analysis set has been re-defined as “all participants who received at least one dose of RLYB212 and at least one RLYB212-PK sample has been analyzed”.

The description of safety analysis set is re-defined as all participants in the study who received any dose of RLYB212 to include participants receiving any amount of the prescribed intervention.

The following analysis sets are added to accommodate summary or listing requirements (see [Table 1](#) for detailed description each analysis set).

- Neonate Full Analysis Set (NFAS)
- Immunogenicity Analysis Set (IMAS)
- Full Analysis Set (FAS)

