4.9. Changes in the Conduct of the Study or Planned Analyses

In response to a directive from the Sponsor, Rallybio IPA, LLC, a strategic reduction in the scope of the Tables, Listings, and Figures (TLFs) described in the current SAP was implemented for the final analysis.

The study was terminated early. The decision was based on pharmacokinetic (PK) data from the Phase 2 trial demonstrating the inability of the RLYB212 dose regimen to achieve the predicted

target concentration range, as well as the minimum concentration required for efficacy. As a result, the Sponsor discontinued further development of RLYB212.

Given the early termination and the limited sample size (only one participant enrolled), the originally planned statistical analyses and TLFs will not be produced. Instead, participant-level listings will be generated to present the data collected up to the time of study termination. These listings will include participant disposition, inclusion/exclusion criteria, protocol deviations, demographics characteristics, pregnancy outcome, newborn and infant general status, medical and obstetric history, prior and concomitant medication, study drug exposure, adverse events, laboratory results, vital signs, ECG, and relevant efficacy assessments.

No tables, figures, or inferential statistical analyses will be performed. The listings will be descriptive in nature and will serve as the sole presentation of the study data.

5. Sample Size Determination

The primary objectives of the study are to characterize the safety and PK of RLYB212 in HPA-1b/b pregnant women at risk of HPA-1a alloimmunization. Empiric PK data from this study will be used to supplement the parameters for the current clinical pharmacology model, including the impact of target-mediated drug disposition, if necessary. The PK characterization of RLYB212 in this study is intended to be exploratory, rather than to meet a pre-specified statistical objective. The proposed sample size of 8 is consistent with other studies reported in literature intended to characterize the PK of monoclonal antibodies in an exploratory manner and has been determined to be adequate from a PK perspective based on the following (refer to protocol section 9.2 for details).

- Low to moderate variability observed in RLYB212 PK.
- Antibody PK in pregnancy.
- Conservative dose selection approach.

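### A cord-blood RLYB212 value below the quantification limit would be listed as 0, while the mother's unquantifiable values are listed as NQ

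*SAP*

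**What the plan says.** SAP 4.3.1.1 covers the secondary endpoint of neonatal exposure. On presentation it says "Neonate serum concentration will be listed only for all newborns for the RLYB212 PK analysis set", and on results below the quantification limit it says "Serum concentrations below BLQ will be imputed as 0". Protocol 9.4.3 describes the data behind it: "RLYB212 exposure in the neonate will be evaluated by cord blood concentration of RLYB212, which will be a single measurement".

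For the mother, SAP 4.2.1.1 says "Individual concentrations below the LLOQ of the bioanalytical assay will be reported as NQ (Not Quantifiable) in the listings", with the LLOQ to be given in the footnotes. Where the SAP uses zero elsewhere, it says what the zero is for. In 4.1.3.4, missing or unquantifiable pre-dose results "will be imputed as zero for graphing and descriptive statistics of concentrations", and the last zero rule in 4.2.1.1 is likewise confined to descriptive summaries.

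SAP 4.8 widens the PK analysis set because "there is a formal possibility of (all) samples reading below LLOQ, and that is important information".

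SAP 4.9, added after early termination with one participant enrolled, drops the planned tables and figures. Participant-level listings remain, and these "will serve as the sole presentation of the study data". The list of their contents ends with "adverse events, laboratory results, vital signs, ECG, and relevant efficacy assessments" and nowhere names RLYB212 concentrations. SAP 1.1.1 still promises that drug concentrations will be both summarised and listed in the study report.

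**The concern.** A result below the LLOQ says that the concentration lies somewhere between 0 and the LLOQ. Printing 0 replaces that interval with a single value and reads as a finding of no drug. Printing NQ beside the LLOQ says what the assay can support. Under the plan as written, mother and newborn could have the same kind of result for the same drug and be reported in two different ways.

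The newborn's value carries the whole objective. There is one endpoint for neonatal exposure and one measurement of it, so no other figure would correct a misleading one. An unquantifiable result is also not far-fetched: 4.9 says the study stopped because the regimen did not reach the target concentration range.

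There is a further, conditional reason for care. Protocol 2.2.2.1 notes that the nonclinical assay detects only free drug, which limited exposure assessment in antigen-positive animals. The documents do not say whether the clinical assay works the same way. If it does, an unquantifiable cord result from an HPA-1a positive newborn could reflect binding rather than absence, and 0 would be a poor label for it.

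**Working it through.** There is no sample size or power figure to reproduce here. The check is a comparison of the SAP's own rules, followed by a bound on the effect.

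**Step 1. The rules side by side**

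| SAP section | Value | Rule below LLOQ | Where the rule acts |
|---|---|---|---|
| 4.1.3.4 and 4.2.1.1 | Maternal, pre-dose | Zero | Graphs and descriptive statistics |
| 4.2.1.1, final rule | RLYB212 concentration | Zero | Descriptive summaries |
| 4.2.1.1 | Individual values (maternal section) | NQ, LLOQ footnoted | Listings |
| 4.3.1.1 | Cord blood | Zero | Not stated; only a listing is planned |

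Every zero rule outside 4.3.1.1 is tied to a graph or a statistic. For cord blood neither exists, so if the rule does anything it changes the listed value. That is the one place where the maternal section calls for NQ.

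**Step 2. Consistency with 4.8.** The PK analysis set was redefined so that participants with only unquantifiable samples stay in, because those readings matter. A listed 0 would then hide that the reading was below the LLOQ.

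**Step 3. Does the cord value reach the final report?** Section 4.9 does not name it. Laboratory results could cover maternal PK, which sits under the laboratory heading in Table 3, and PK has a row in Table 5. In Table 3 the cord-blood sample sits under other assessments instead. Section 1.1.1 points towards a listing, but it also promises summaries that 4.9 removes. The question is open.

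**Step 4. Size**

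- Participants enrolled: 1 (SAP 4.9).
- Fetuses per participant: 1 (multiple pregnancy is excluded, Protocol 5.2.2).
- Cord measurements per newborn: 1 (Protocol 9.4.3).
- Maximum affected values = 1 × 1 × 1 = 1.
- Possible misstatement: from 0 up to the LLOQ. Neither document gives the LLOQ, so this cannot be put in ng/mL.

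**Related text errors.** These add no weight to the point, because they do not affect the final report while 4.9 stands.

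- Section 4.2.1.1 gives three treatments for a post-dose maternal value below the LLOQ (missing, set to the LLOQ, or 0) with no order of precedence. The pre-dose zero also conflicts with the rule that reports NQ when all values at a time point are unquantifiable.
- In Table 4 the Week 20 limits run from Day 143 to Day 137 in 4 rows (ultrasound, drug administration, ADA, PK). As printed, each window contains 0 days.
- The Visit 13 ultrasound window, Day 151 to Day 153, omits its own target, Day 154.
- The Table 4 footnote counts the dosing day as Day 1, so week *w* should fall on Day 7*w* + 1. For Weeks 2, 4, 8, 10, 12, 14, 16, 18, 20 and 22 the printed target is 7*w* (14 to 154) rather than 7*w* + 1 (15 to 155). That is 1 day early in 10 of 10.

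**The case against.** The strongest reply is that 4.3.1.1 no longer governs anything. The SAP version history says the analyses and outputs of the original SAP will not be performed, and 4.9 replaces them with listings of the data collected. A listing of collected data would most naturally show the reported result, not an imputed one. The SAP also separates imputed from displayed values in another setting: 4.1.3.4 keeps imputed dates out of the listings. On that view the cord sentence is leftover text with no effect. The NQ rule, though placed in the maternal section, is worded for individual concentrations in general and could be read to cover cord blood.

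The reply also has force on 4.9. Its list of contents says what the listings include and need not be exhaustive, and a cord-blood assay can fairly be called a laboratory result.

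Part of this stands. The harm needs a chain that the documents do not establish: a cord sample was obtained, it read below the LLOQ, it was listed, and it was printed as 0. It is also fair that the Table 4 errors say nothing about cord blood.

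The rest does not remove the problem. Section 4.9 keeps listings as the only output and gives no new rule for values below the LLOQ, so the sentence in 4.3.1.1 is still the only one written for cord blood. The rule on imputed dates covers dates alone. If the NQ rule does extend to cord blood, the SAP holds two conflicting instructions for one listing.

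**Conclusion.** The point holds, and it is minor. As written, the SAP would show an unquantifiable cord-blood concentration as a measured zero, contrary to its own maternal listing rule and to its reasoning in 4.8. At most one value is affected, by an amount between 0 and an LLOQ that the documents do not give. Development has stopped, and no decision is shown to turn on the value.

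The conclusion rests on two conditions: that the cord value is listed in the final report, which 4.9 leaves unclear, and that it reads below the LLOQ, which is unknown. The mismatch between the rules is certain; the consequence is only possible.

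**What to change.** - **4.3.1.1:** replace the zero rule with a sentence saying that cord-blood concentrations below the LLOQ will be listed as NQ, with the LLOQ in the footnote.
- **4.9:** name the maternal and cord-blood RLYB212 concentration listings among the outputs.
- **1.1.1:** align the sentence on drug concentrations with 4.9, so that it no longer promises a summary.

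The cost is one sentence and two phrases, with no new data or analysis.

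If the superseded text is kept, two further corrections are worth making at the same time. In 4.2.1.1, keep one rule for post-dose values below the LLOQ and state the pre-dose zero as an explicit exception to the NQ rules. In Table 4, first reconcile the target days with the Day 1 convention in the footnote, then reset the reversed and truncated windows.
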